PET/CT or CT scans	X					X ^m		X ⁿ	X ^o	X	X ^h
Bone marrow biopsy and aspirate	X ^p							X ^q	X ^q		X ^q
Histologic review	X ^r										
Correlative studies	See Correlative Study Calendar										

- Initial medical history should include: baseline symptoms; a detailed history of prior cancer therapies including start and stop dates, disease progression during or after therapy, as well as discontinuations due to intolerability or any other serious illness; family and social history; calculation of Rai Stage (for CLL patients), MIPI (for MCL patients), or IPI (NHL patients other than MCL; see Appendix C).
- Progress notes should include: new symptoms or adverse events, ECOG performance status (Appendix A), documentation of physical exam, status of disease.
- Ophthalmologic exam: required at screening, if clinically indicated during study, and at final visit. Prior to dilation: best corrected visual acuity, visual field examination via automated perimetry, tonometry, and color vision test. Dilated funduscopy and slit lamp exam including anterior segment photos to document lens clarity.
- For ECOG performance status, see Appendix A
- Prothrombin time, international normalization ratio, and activated partial thromboplastin time
- Sodium, potassium, bicarbonate, BUN, calcium, chloride, creatinine
- Albumin, alkaline phosphatase, total bilirubin, total protein, SGOT [AST], SGPT [ALT]
- FISH panel will use probes to detect for abnormalities in chromosomes 13q, 12, 11q, and 17p.
- For CLL patients only.
- Pregnancy tests for females of childbearing potential. A female of childbearing potential (FCBP) is a sexually mature female who: 1) has not undergone a hysterectomy or bilateral oophorectomy; or 2) has not been naturally postmenopausal (amenorrhea following cancer therapy does not rule out childbearing potential) for at least 24 consecutive months (i.e., has had menses at any time in the preceding 24 consecutive months). Female of childbearing potential must have a negative serum β -Hcg pregnancy

test result within 3 days of first study dose.

- k. For cycles 7 and higher, patient will be required to return for evaluation and to receive KPT-330 every 3rd month (eg. Cycle 7 Day 1, Cycle 10 Day 1, Cycle 13 Day 1....)

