- l. Reassessment off therapy will occur 4 weeks from the last dose of study therapy. For patients removed from study for reasons other than disease progression, reassessment will then occur then every 6 months until progression or an alternative therapy is started.
- m. Cycle 2 Day 1 only.
- n. Cycle 4 Day 1 only.
- o. Restaging scans and immunophenotyping will be performed every 3 cycles for the first year and then every 6 months thereafter.
- p. Bilateral bone marrow biopsies are preferred for lymphoma patients.
- q. A bone marrow biopsy and aspirate should be performed to confirm a complete response if there was bone marrow involvement at diagnosis, clinical MRD flow should be performed in this case.
- r. For patients with DLBCL only: Paraffin block must be submitted for immunohistochemistry evaluation of CD10, bcl-6, and MUM-1 to determine ABC vs GCB subtype. Biopsy to confirm histologic review does not need to be repeated for pre-study requirements, so long as previously obtained tissue confirms patient meets histologic eligibility criteria prior to study registration.

OSU Protocol #:14087

Version 7

Date: 03 August 2021

Cohort 3 Study

Calendar

Cycle	Pre-Study	Day 1, Cycles 1-3	Day 1, Cycles 6, 9, 12	Cycle 14 Day 1	Day 1, every 3 cycles following cycle 14 (continue ibrutinib) C17, 20, 23, 26, etc.	Day 1, every 3 cycles following cycle 14 (off therapy)	Follow-up (off therapy) ^j
Eligibility checklist	X						
Informed consent	X						
History ^a	X						
Progress note ^b		X	X	X	X	X	X
Physical exam	X	X	X	X	X	X	X
Ophthalmologic exam ^c	X						
Concurrent meds	X	X	X		X		
Vital signs/weight/height/BSA	X	X	X		X	X	
ECOG ^d	X	X	X		X	X	
CBC, dif, platelets	X	X	X		X	X	
Coagulation ^e	X	X	X		X		
Chemistry ^f , Ca, Mg, Phos	X	X	X		X	X	
Liver function tests ^g	X	X	X		X		
LDH	X						
Uric acid	X						
Peripheral blood immunophenotyping	X		X			X	X
Quant immunoglobulins	X		X				
SPEP with immunofixation							

CLL karyotype, FISH panel ^h & IgVH mutational analysis ^h	X						
Pregnancy test ⁱ	X						
HIV/Hep	X						
Buccal swab	X						
ECG	X						
Adverse event evaluation	X	X			X		
PET/CT or CT scans	X					X ^k	X
Bone marrow biopsy and aspirate	X			X			
Correlative studies	X	X	X	X	X	X	

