- With the exception of splenic and hepatic nodules, involvement of other organs is usually assessable and no measurable disease should be present.
- Bone marrow assessment is irrelevant for determination of a PR if the sample was positive before treatment. However, if positive, the cell type should be specified (e.g., large-cell lymphoma or small neoplastic B cells). Patients who achieve a CR by the above criteria, but who have persistent morphologic bone marrow involvement, will be considered partial responders. When the bone marrow was involved before therapy and a clinical CR was achieved, but with no bone marrow assessment after treatment, patients should be considered partial responders.
- No new sites of disease should be observed.
- If performed, the post-treatment PET should be positive in at least one previously involved site.

Stable Disease (SD):

Patient fails to attain the criteria needed for a CR or PR, but does not fulfill those for progressive disease (see below). If performed, the PET should be positive at prior sites of disease, with no new areas of involvement on the post-treatment CT or PET.

Progression (PD) or Relapse:

- Lymph nodes should be considered abnormal if the long axis is > 1.5 cm, regardless of the short axis. If a lymph node has a long axis of 1.1 to 1.5 cm, it should only be considered abnormal if its short axis is > 1.0 . Lymph nodes ≤ 1.0 by ≤ 1.0 will not be considered as abnormal for relapse or progressive disease.
- Appearance of any new lesion > 1.5 cm in any axis during or at the end of therapy, even if other lesions are decreasing in size. Increased FDG uptake in a previously unaffected site should only be considered relapsed or progressive disease after confirmation with other modalities. In patients with no prior history of pulmonary lymphoma, new lung nodules identified by CT are mostly benign. Thus, a therapeutic decision should not be made solely on the basis of the PET without histologic confirmation.
- At least a 50% increase from nadir in the SPD of any previously involved nodes, or in a single involved node, or the size of other lesions (e.g., splenic or hepatic nodules). To be considered progressive disease, a lymph node with a diameter of the short axis of $<$

1.0 cm must increase by $\geq 50\%$ and to a size of 1.5 x 1.5 cm, or > 1.5 cm in the long axis.

- At least a 50% increase in the longest diameter of any single previously identified node > 1.0 cm in its short axis.

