Lesions should be PET-positive if a typical FDG-avid lymphoma or the lesion was PET- positive prior to therapy unless the lesion is too small to be detected with current PET systems (< 1.5 cm in its long axis by CT).

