11.1.5 Progression-Free Survival

PFS is defined as the duration of time from start of treatment to time of progression or death, whichever occurs first.

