13.5 Definition of Secondary Endpoints

13.5.1 Toxicity will be graded by CTCAEv4.0. A copy of the CTCAE version 4.0 can be downloaded from the CTEP web site
http://ctep.cancer.gov/protocolDevelopment/electronic_applications/ctc.htm.

13.5.2 Clinical response and survival will be measured by:

- International Working Group Criteria for NHL patients.
- IWCLL 2008 Guidelines for CLL patients.

Response criteria are detailed in Section 10.

Responders will be defined as those with complete response (CR) or partial response (PR). Overall response rate (ORR) will be calculated as the number of evaluable responders divided by the total number of evaluable patients and will be analyzed by cohort. All patients who receive at least one dose of study medication will be included in the ORR and progression free survival.

Progression Free Survival (PFS): PFS will be calculated from the date of study enrollment to disease progression or death, whichever occurs first. Patients who do not progress or die will be censored at the time of last contact with response assessment by physical exam and laboratory studies.

Overall Survival (OS): OS will be calculated from the date of study enrollment to death. Patients who do not die will be censored at the time of last contact. This will be analyzed in each cohort independently.

13.5.3 Response as related to chronic lymphocytic leukemia (CLL) karyotype and IgVH mutational status. Response criteria are detailed in Section 10.

13.5.4 For Cohort 3, the rate of deepening of response is defined as the percentage of patients who attain a MRD negative complete response (MRD- CR) at the end of 14 cycles of selinexor plus ibrutinib.

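### The PFS censoring rule names only physical exam and laboratory studies, although NHL progression is judged mainly by lesion measurement and PET/CT, so an NHL patient with a missed scan can be credited with unverified progression-free time.

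*Combined protocol and SAP*

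**What the plan says.** **Endpoint and censoring (13.5.2).** "PFS will be calculated from the date of study enrollment to disease progression or death, whichever occurs first". Patients with neither event are "censored at the time of last contact with response assessment by physical exam and laboratory studies". There is one rule for both diseases, imaging is not named, and everyone who takes at least one dose is included. Section 11.1.5 also defines PFS but gives no censoring rule, and no other section ties censoring to a scan.

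**NHL progression (11.1.2).** The criteria include "Appearance of any new lesion > 1.5 cm in any axis during or at the end of therapy" and "At least a 50% increase from nadir in the SPD of any previously involved nodes", with a PET condition: "Lesions should be PET-positive if a typical FDG-avid lymphoma".

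**Calendar (section 10, dose escalation and expansion).** Exam and laboratory tests are due at every visit. Scans are due on Day 1 of Cycles 2 and 4 (footnotes m and n). From Cycle 7, footnote o applies: "Restaging scans and immunophenotyping will be performed every 3 cycles for the first year and then every 6 months thereafter". Footnote k sets the visits from Cycle 7: "patient will be required to return for evaluation and to receive KPT-330 every 3rd month". A scan is also marked in the Off Treatment and Follow-up columns.

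**Use (13.8.2).** PFS at the MTD is described by Kaplan-Meier curves for each disease group.

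**The concern.** A censoring date should be the last date on which the patient was shown to be free of the event. For CLL, exam plus blood counts is a reasonable standard, because a rise in blood lymphocytes can itself define progression (11.1.3). For NHL it is not: an exam may find a new palpable node, but exam and laboratory tests cannot exclude growth or new disease at sites that need imaging.

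Read as written, the rule lets an NHL patient whose scan was missed, but whose visit was kept, stay in the risk set as progression-free. That enlarges the denominator when other patients progress and raises the curve. Sections 2.4 and 2.5 quote single-agent ibrutinib PFS figures (13.9 months in MCL; 5.5 months in ABC-DLBCL responders), and readers are likely to set the NHL curve beside them.

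**Working it through.** The plan gives no sample size, event count or test for PFS, so there is no figure of its own to reproduce.

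**Step 1. Unscanned time the calendar allows.** Weeks from Cycle 1 Day 1 = 4 × (cycle − 1), plus 2 for Day 15. Six months is taken as six cycles. The gap is the visit week minus the week of the last scan.

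| Visit | Week | Last scan (week) | Gap |
|---|---|---|---|
| C3D15 | 10 | C2D1 (4) | 6 weeks |
| C6D1 | 20 | C4D1 (12) | 8 weeks |
| C7D1, C10D1, C13D1 | 24, 36, 48 | same day | 0 |
| C16D1 | 60 | C13D1 (48) | 12 weeks |

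The last gap recurs at alternate visits after year 1. A missed scan lengthens it: if the C19D1 scan (week 72) is missed and the patient is last seen at C22D1 (week 84), the gap is 84 − 48 = 36 weeks.

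**Step 2. When the gap moves the curve.** With every scan on schedule, detected progressions fall on common scan dates. A patient censored between two scans is out of the risk set at the later one under either rule, so the estimate does not change. It changes when a patient misses a scan that others have and is still counted at risk on that date.

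**Step 3. Simulation at 50 weeks.** Assumptions: 10 NHL patients, 3,000 replicates, exponential PFS with the protocol's two medians used only as scenarios, cut-off uniform over weeks 12 to 100, each scan missed independently with the visit kept, and no exit scan.

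| Scans missed | Median 5.5 months: stated rule / last scan | Median 13.9 months: stated rule / last scan |
|---|---|---|
| 0% | 25.5% / 25.5% | 57.5% / 57.5% |
| 10% | 26.7% / 25.7% | 58.9% / 58.1% |
| 20% | 28.0% / 25.5% | 60.4% / 58.4% |
| 30% | 30.4% / 26.0% | 62.1% / 58.5% |

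Mean extra time credited per censored patient is 3.1 to 3.5 weeks with none missed and 10.1 to 10.6 weeks with 30% missed.

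Benchmark: the last scan before week 50 is at week 48, so the true value on the scan schedule is 2^(−48/m), where m is the median in weeks (months × 4.345).

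- Median 5.5 months: m = 23.9, giving 2^(−2.01) = 24.9%.
- Median 13.9 months: m = 60.4, giving 2^(−0.795) = 57.6%.

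At 30% missed, last-scan censoring is 26.0 − 24.9 = 1.1 and 58.5 − 57.6 = 0.9 points above this. The stated rule is 30.4 − 24.9 = 5.5 and 62.1 − 57.6 = 4.5 points above.

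**Step 4. Simulation at 18 months, 40% yearly dropout.** There is no difference if scans are on schedule or an exit scan is done. With no exit scan, the stated rule is about 1 to 3 points higher with 15% of scans missed and about 3 to 4 points higher with 30% missed. Last-scan censoring is then closer to the truth.

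**The case against.** **The rule refers to a response assessment, not to any visit.** A reader might infer that every blood draw, including the weekly ones in Cycle 1, moves the censoring date. The text does not go that far. Section 11.1 schedules response assessments at 1 and 3 months, then 3-monthly for a year, then 6-monthly, and the protocol overview names PET/CT, CT and/or immunophenotyping as the means. On that reading several gaps in Step 1 disappear. What stands is that 13.5.2 states how the qualifying assessment is made, and imaging is not part of it. A response visit with the scan missed would still qualify.

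**An exit scan is required.** This is correct, and where it is done the difference between the rules is at most about 0.1 point, even with 30% of scheduled scans missed. The effect needs patients who skip it.

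**A general upward bias is not shown.** A reader might infer that NHL PFS is inflated in any case. With no missed scans, the result depends on the set-up: 0.8 to 2.2 points higher in runs that add small cycle delays, no change on the exact calendar, and 0.4 to 1.5 points lower in one set-up without delays or exit scan. No direction can be claimed there.

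**Last-scan censoring is not free of error.** In runs with cycle delays it can undershoot. One no-missed-scan scenario gave 0.386, against a true 18-month value of 2^(−18/13.9) = 0.408, which the stated rule reproduced. The handling of late and missed scans should therefore also be stated.

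**CT/PET is not the sole basis of NHL progression.** The criteria are lesion sizes with PET/CT conditions, so a palpable new node could count. Exam and laboratory tests still cannot rule progression out.

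**Little rests on PFS.** No test or decision rule uses it. For scale, the exact 95% interval for 4 of 10 runs from 12% to 74%, far wider than the shift.

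**Conclusion.** The censoring wording in 13.5.2 does not match the NHL progression criteria in 11.1.2, and nothing elsewhere repairs it. The consequence is conditional. The NHL Kaplan-Meier estimate is essentially unchanged when scans are on schedule or the exit scan is done. With 15% to 30% of scans missed and no exit scan, 18-month PFS is higher by roughly 1 to 4 points. The documents give no dropout or missed-scan rates; these, and the exponential PFS model, are assumptions. With a descriptive secondary endpoint in about 10 NHL patients, the impact is modest. The change is worth making because it is cheap and removes an ambiguity.

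**What to change.** In 13.5.2, replace the common censoring sentence with one for each disease:

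- *NHL: patients without progression or death are censored at the last adequate CT or PET/CT assessed by 11.1.2 and showing no progression, or at the PFS time origin if there is no post-baseline scan.*
- *CLL: the qualifying assessment remains physical exam plus blood counts.*

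Add a line on how late and missed scans are handled. The time origin must be the one used for PFS. Section 13.5.2 counts from enrollment, whereas 11.1.5 says "PFS is defined as the duration of time from start of treatment to time of progression or death, whichever occurs first", and section 4 allows up to 7 business days between registration and treatment. That difference is a separate point, but it has to be settled for this wording to work.

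Cost: a text change with no new data. Some NHL follow-up time is lost, and the PFS estimate may be slightly lower.

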13.6 Definition of Exploratory Endpoints

13.6.1 Pharmacodynamic endpoints for patients with CLL include:

- Markers of downmodulation or inhibition of the B-cell receptor pathway including BTK expression and phosphorylation of SYK, AKT, and ERK will be assessed pretreatment and post-treatment where feasible, and reported as a continuous measure.
- Change in localization of tumor suppressor and oncogene proteins and mRNAs (P53, p73, Bcl-2, c-myc, Bcl-6, NFκB/IκB, FOXO3a and FOXO1) will be assessed pretreatment and post-treatment where feasible. Change in localization will be measured through blood sample collection, analyzed by immunoblot, and reported as percentage of protein fragments observed in the nucleus at each time point.
- Potential predictive biomarkers will be assessed before and after in vitro treatment of patients' pretreatment leukocytes via qRT-PCR and results will be reported as fold change from baseline.

13.7 Analytic Plan for Primary Objective

The primary objective is to identify the highest dose level of selinexor administered with ibrutinib that corresponds to an acceptable probability of DLT, defined as <0.30, in relapsed/refractory CLL and NHL patients. We do not expect that toxicity will be different between CLL and NHL, thereby justifying the use of both groups in dose escalation. Dosing

decisions will be made throughout the course of the trial based on a modified continual reassessment method (MCRM),⁴³⁻⁴⁵ combining information assumed *a priori* with observed data to update the estimate of the true dose-toxicity curve. *A priori*, it is assumed that the dose toxicity curve is monotonically increasing and belongs to the family of two-parameter logistic models, allowing the scale and slope to vary as described by Piantadosi et al.⁴⁵ To implement the model, including input of prior assumptions, data collection, and estimation of the dose-toxicity curve, software developed by Piantadosi (Modified Continual Reassessment Method, version 4.0) will be used. For model initiation, the *a priori* curve has been defined using three coordinates elicited from the clinical investigators to represent a “safe”, “moderately risky” and “risky” weekly dose level of selinexor when combined with the standard dose of ibrutinib in this patient population (Figure 2). The information represented in the *a priori* curve is equivalent to that of only 1.5 subjects, and hence, observed data accumulated throughout the trial is expected to outweigh any pseudo-data pre-specified when making dosing decisions. The target dose for each cohort will be identified by the software, but the starting dose and dose escalation will be constrained by design to ensure safety, as suggested in Garrett-Mayer’s 2006 tutorial, using the following rules: 1) the starting dose level will be the lowest dose level, 2) the dose level assigned for each successive cohort will be the highest dose level less than or equal to the target dose identified by the software provided there is not escalation by more than one dose level; otherwise, the target dose identified by the software will be disregarded and an increase in only one dose level at a time will be permitted, and 3) in the absence of DLT, decisions will be made following cohorts of 2 or 3 patients, cohort sizes that have been shown to balance accurate MTD information and safety.⁴⁶ We will only escalate dosing when $\leq 33\%$ of patients at a dose level experience DLT, and patients will not be assigned to an escalated dose level if there is a high probability that the DLT rate at that dose level is $>30\%$. It is planned that groups of 2 patients will be treated at lower dose levels of selinexor and groups of 3 patients will be treated beginning with dose level 3 in order to expedite the dose finding process. The trial will stop when the MCRM is deemed to have adequately converged on an MTD. Specifically, the trial will stop when 10-12 patients (depending on cohort size) are treated at a particular dose level which is also subsequently a suggested dose level by the model *or* a maximum of 36 evaluable patients have been treated, whichever occurs first (approximately 6-14 cohorts). At the time the trial terminates, the MTD will correspond to the highest dose level with probability of DLT <0.30 . The MCRM process will be summarized, including number of DLTs observed in each cohort and the recommended dose at the end of each cohort. Using the parameter and covariance estimates from the model, and assuming parameters are from a bivariate normal distribution, repeated sampling will be used to construct an empirical distribution of the probability of DLT at the selected dose level to obtain 95% confidence intervals. At the MTD, we will accrue up to 10 CLL patients and 10 NHL patients in an expansion.

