5.3 Definition of Dose Limiting Toxicity

CTCAE version 4.0 is used to grade all adverse events and to provide management guidelines for administrative toxicity. A copy of the CTCAE version 4.0 can be downloaded from the CTEP web site http://ctep.cancer.gov/protocolDevelopment/electronic_applications/ctc.htm.

Definition of DLT for patients receiving selinexor and ibrutinib*	
General	

 Treatment delays >28 days for any toxicity Any grade 5 toxicity 	
Non-hematologic	

 Grade 3 nausea/vomiting or diarrhea lasting for ≥ 7 days while taking optimal supportive medications# Grade 3 anorexia or fatigue lasting for ≥ 7 days while taking optimal supportive care# and with correction of dehydration, anemia, endocrine, or electrolyte abnormalities Grade ≥ 3 AST or ALT elevation lasting for ≥ 7 days OR any Grade ≥ 3 AST or ALT elevation in the setting of bilirubin elevation $> 2 \times$ ULN Any other Grade 3 non-hematological toxicity except alopecia, rash that resolves to Grade 1 in ≤ 7 days, or electrolytes abnormalities correctable with supportive therapy# Any Grade 4 non-hematologic toxicity not specifically listed above 	
Hematologic	

 Grade 4 neutropenia [absolute neutrophil count (ANC) $< 500/\text{mm}^3$] (for patients with baseline ANC $\geq 1000/\text{mm}^3$) or $\geq 75\%$ reduction of neutrophils (for patients with baseline ANC $< 1000/\text{mm}^3$) lasting ≥ 7 days; Grade 4 thrombocytopenia [platelet count $< 25,000/\text{mm}^3$] (for patients with baseline platelets $\geq 100,000/\text{mm}^3$) $\geq 75\%$ reduction of platelets (for patients with baseline platelets $< 100,000/\text{mm}^3$) that persists for ≥ 7 days; Grade ≥ 3 thrombocytopenia-associated bleeding; or Grade 4 febrile neutropenia (ANC $< 1000/\text{mm}^3$ with a single temperature $\geq 38.3^\circ\text{C}$ or sustained temperature of $> 38^\circ\text{C}$ for over 1 hour). 	
*Assessed during Cycle 1 by CTCAEv4 criteria #Section 4.4 provides detailed supportive care ^For patients with Gilbert's syndrome: $> 2 \times$ baseline	

AEs meeting the above definitions but that are clearly unrelated to study drugs will not be considered DLTs.

Patients will be considered eligible for DLT assessment if they receive at least 2 of 3 planned doses of selinexor and 19 of 21 planned doses of ibrutinib.

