In rare instances, an event may fall within the definition of a DLT as defined above, but the event may not be considered a DLT (ie: not clinically meaningful/significant). If this occurs, a meeting

with all investigators, PI and Sponsor will take place to thoroughly review the event and supporting data and the reasons for not considering the event a DLT will be clearly documented with supporting rationale. Conversely, other events may occur which do not meet the definition of a DLT but are concerning to the investigators and sponsor and may be then considered to be DLTs. We will also consult the DSMC team for input.

Management and dose modifications associated with the above adverse events are outlined in Section 5.

Dose escalation will proceed within each cohort according to the following scheme. Dose-limiting toxicity (DLT) is defined above.

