6. DOSING DELAYS/DOSE MODIFICATIONS

Toxicities that occur in cycle 1 that are DLTs (Section 4.2) will result in protocol removal. Adverse events that are not defined as DLTs and / or occur in cycles 2 and higher will lead to dose delays and modifications as detailed below. No dose reduction below ibrutinib 140 mg and selinexor 20 mg/week will be allowed. If a patient experiences several adverse events, and there are conflicting recommendations, the investigator should use the recommended dose adjustment that reduces the dose to the lowest level. Missed doses will not be replaced. Treatment delays for adverse events exceeding 28 days will lead to protocol removal unless approved by the principal investigator.

Ibrutinib-related lymphocytosis, for the purposes of this protocol, is defined as an elevation in blood lymphocyte count of $\geq 50\%$ compared with baseline count in conjunction with unequivocal improvement in at least 1 other disease-related parameter including lymph node size, spleen size,

hematologic parameters (hemoglobin or platelets), or disease-related symptoms. Ibrutinib-associated treatment-related lymphocytosis generally occurs within the first few weeks of therapy, peaks within the first few months, and resolves slowly. Patients with isolated lymphocytosis in the setting of reduced disease burden or improvement in hemoglobin/platelets should not be considered to have progressive disease.

Asymptomatic treatment-related lymphocytosis should not be considered an adverse event. Subjects with treatment-related lymphocytosis in the absence of other disease-related symptoms should be encouraged to remain on study treatment and continue with all study-related procedures.

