7.14 Data Safety Monitoring Plan

The data and safety monitoring plan will involve the continuous evaluation of safety, data quality and data timeliness. Investigators will conduct continuous review of data and patient safety at their regular Disease Group meetings (at least monthly) and the discussion will be documented in minutes. For each dose level, the Principal Investigator, study coordinator, and statistician, in consultation with treating physicians as appropriate will review all toxicities at a given dose level to inform the model for dose level adjustments. The Principal Investigator of the trial will review toxicities and responses of the trial where applicable at these disease center meetings and determine if the risk/benefit ratio of the trial changes. Frequency and severity of adverse events will be reviewed by the Principal Investigator and compared to what is known about the agent/device from other sources; including published literature, scientific meetings and discussions with sponsors, to determine if the trial should be terminated before completion. Serious adverse events will be reviewed by the OSUCCC Data and Safety Monitoring Committee (DSMC). The Principal Investigator will also submit a biannual progress report that will be reviewed by the committee per the DSMC plan. All reportable SAEs will be reported to the IRB of record as per the policies of the IRB.

Mandatory safety and trial review teleconferences will be scheduled and moderated by the Multi-Center Trial Program (MCTP). All sites involved in the study are expected to have a representative present every month to review and discuss patients on study and other applicable agenda items. Meeting minutes will be used to document each monthly teleconference. The minutes will be stored in the MCTP protocol files.

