13. STATISTICAL CONSIDERATIONS

13.1 Study Design

Cohorts 1 and 2 of this study represent a prospective, multi-center, phase I dose escalation study in two diseases: CLL and NHL. Dose-finding will proceed using a modified continual reassessment method and targeting a probability of $DLT < 0.30$. To ensure safety, the starting dose level will be the lowest dose level and dose escalation will proceed by increasing only one dose level at a time. Groups of 2-3 patients will be treated until convergence on an MTD, defined as 10-12 patients treated at a particular dose level which is also a subsequently suggested dose level by the model *or* a maximum of 36 evaluable patients, whichever occurs first. At the MTD, up to 10 CLL patients and 10 NHL patients will be accrued.

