13.3 Evaluability

Any patient who is eligible for the trial and has received at least one dose each of the selinexor and ibrutinib will be evaluated for toxicity (descriptive summary as well as dose escalation determination in the first two cohorts) and for response. Patients who are not evaluable for toxicity at a given dose level will be replaced.

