
13.8 Analytic Plan for Secondary Objectives

13.8.1 Toxicity

Toxicities will be tabulated by type and grade and displayed in summary form. In addition, the number of cycles started/completed, number of patients requiring dose reductions, and the reason for going off treatment may be summarized to assess treatment tolerability.

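### Section 13.7 does not say whether DLTs in the expansion count towards the final DLT estimate at the MTD; a pooled rate with an exact interval would be more precise at almost no cost

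*Combined protocol and SAP*

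**What the plan says.** Section 13.7 takes its steps in this order. Dose finding stops when 10-12 patients have been treated at a level that the model suggests again, or at 36 evaluable patients. The MTD is then the highest level with a DLT probability below 0.30. A 95% interval for that probability is built by sampling from the fitted model parameters. The section ends: "At the MTD, we will accrue up to 10 CLL patients and 10 NHL patients in an expansion". Section 13.1 has the same order: "At the MTD, up to 10 CLL patients and 10 NHL patients will be accrued". Neither section says how DLTs in the expansion are analysed.

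For toxicity outside the model, 13.8.1 says: "Toxicities will be tabulated by type and grade and displayed in summary form". That gives a table of events, not a DLT rate.

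Three passages bear on who counts:
- Section 5.3: "Patients will be considered eligible for DLT assessment if they receive at least 2 of 3 planned doses of selinexor". It also asks for 19 of 21 ibrutinib doses.
- Section 13.3 asks only for one dose of each drug. It applies to the descriptive summary and to "dose escalation determination in the first two cohorts".
- Section 6: "Toxicities that occur in cycle 1 that are DLTs (Section 4.2) will result in protocol removal".

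**The concern.** DLT is the primary endpoint (13.4), and the primary conclusion is a dose whose DLT probability is below 0.30. The synopsis gives a fuller description of toxicity as one purpose of the expansion, which may roughly double the number treated at the chosen dose. If the interval is fixed when dose finding ends, it rests on 10-12 patients at that dose and its upper limit can exceed 50%, although further cycle-1 DLT data will be collected. If the plan means to pool, it does not say so, and two analysts could report different primary results from the same data. By contrast, 13.8.2 defines the response rate for the patients treated at the MTD, with an exact interval.

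A second gap affects any pooled rate. A patient removed at an early DLT may never reach the 5.3 dose minimum. Read literally, the rule would drop the very patients who had the event.

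**Working it through.** **The plan's own totals.** These show how many patients may be treated at the MTD. Section 13.2 expects about 9 groups of 2-3 patients and 32 patients on average.
- With a midpoint of 2.5 per group and 20 expansion places, less the 10-12 dose-finding patients already at the MTD: 9 × 2.5 + 20 − 12 = 30.5, and 9 × 2.5 + 20 − 10 = 32.5. The stated 32 lies in this range.
- With no overlap, at 2, 2.5 and 3 per group, the total would be 38, 42.5 and 47.
- The stated maximum of 50 is below 36 + 20 = 56, so it too implies an overlap (6 patients).

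The expected total therefore fits about 20 patients at the MTD in all, made up of 10 + 10 or 12 + 8. This is the base case. The plan implies the overlap but does not quantify it.

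**Precision.** Figure 2 (the prior curve) is not shown, so the model's interval cannot be recomputed. The exact (Clopper-Pearson) binomial interval stands in for it. For k DLTs in n patients, the lower limit is the 2.5% point of Beta(k, n−k+1) and the upper limit is the 97.5% point of Beta(k+1, n−k). The DLT counts are assumed.

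| Patients at the MTD | DLTs | 95% interval | Width (points) |
|---|---|---|---|
| Dose finding only | 2/10 | 2.5-55.6% | 53 |
| With expansion | 4/20 | 5.7-43.7% | 38 |
| Dose finding only | 3/12 | 5.5-57.2% | 52 |
| With expansion | 5/20 | 8.7-49.1% | 40 |
| With expansion, if all 20 are new | 8/32 | 11.5-43.4% | 32 |

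With a Beta(0.45, 1.05) prior (mean 0.30, weight 1.5 subjects as in 13.7), the same pattern appears: 4.0-47.9% becomes 6.8-39.7%, and 7.1-50.9% becomes 9.8-45.2%.

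**What pooling costs.** Let a dose pass if its observed rate is below 30% at the end of dose finding (at most 2 of 10, or 3 of 12). The chance that the pooled observed rate among 20 patients is then 30% or more (at least 6 DLTs) is one minus the ratio P(pass and pooled below 30%) / P(pass):
- True rate 0.20: 1 − 0.632/0.678 = 0.068 for 10 + 10; 1 − 0.728/0.795 = 0.083 for 12 + 8.
- True rate 0.25: 1 − 0.447/0.526 = 0.150 for 10 + 10; 1 − 0.536/0.649 = 0.174 for 12 + 8.

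**Who is counted.** For a patient starting ibrutinib on day 8, the 19th dose falls on day 8 + 18 = 26. A DLT that leads to removal before then fails the 19-of-21 minimum. As an example with assumed counts, dropping two such patients turns 4/20 (20%) into 2/18 (11%). In the other direction, counting two under-dosed patients without a DLT turns 4/18 (22%) into 4/20 (20%).

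**Why a pooled proportion rather than a re-run of the model.** Section 13.7 elicits the prior curve on weekly selinexor dose. The two levels in 5.2.3 are 40 mg once weekly (40 mg per week) and 20 mg twice weekly (2 × 20 = 40 mg per week). On that axis they are the same point, so re-fitting with the expansion data would add little to a simple rate at the chosen dose.

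**The case against.** The strongest reply is that the exclusion is only inferred. The interval sentence has no data cut-off, and the MTD is defined as of the trial's termination, which could mean the end of the whole study. Section 13.2 counts the expansion within cohorts 1 and 2; 13.3 covers any eligible patient with one dose of each drug; 13.7 speaks of data accumulating over the trial; and 7.14 has toxicities reviewed "to inform the model for dose level adjustments". This stands in part. A reader might infer that the plan deliberately leaves expansion DLTs out of the primary estimate, but the documents do not support that. Equally, these passages concern dosing decisions, and none ties expansion DLTs to the final estimate or its interval.

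A reader might also infer that leaving them out risks accepting a toxic dose. At a true rate of 0.40, the chance of reporting a rate below 30% is 17-23% on 10-12 patients and 8-10% when it must also hold in the pooled 20; at 0.50 it is 5-7% and 1-2%. This is a stress case. Nothing in the documents suggests such a rate at the starting level. Section 5.1 shows that the return to dose level 1 was a clinical decision made with the DSMC, not a model-driven acceptance. The drop is a gain only if the pooled estimate can overturn the dose, and no such rule is proposed.

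Nor does the lack of a numeric limit mean that the expansion is unmonitored. Section 7.14 provides regular review, and 5.3 allows that "other events may occur which do not meet the definition of a DLT but are concerning to the investigators and sponsor" may be treated as DLTs.

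Finally, a descriptive expansion is a legitimate phase I choice. That is so, and a pooled rate with an interval is still descriptive.

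**Conclusion.** The point holds as a gap in specification that costs precision. As ordered, 13.7 places the MTD's DLT probability and interval at the end of dose finding, and no text brings in the expansion. In the base case of 20 patients at the MTD, pooling shortens the illustrative interval by about 11 to 15 percentage points and lowers its upper limit from about 56-57% to about 44-49%.

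These figures rest on assumed DLT counts, a binomial stand-in for the two-parameter model, and full DLT evaluability. Fewer evaluable expansion patients would mean a smaller gain, and 20 new ones a larger gain. Because the dose is chosen partly on its dose-finding results, the pooled interval is nominal and should be read as descriptive.

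The evaluability gap is a separate, firmer reading of the text: taken literally, 5.3 and section 6 together can remove early DLTs from the denominator and the numerator.

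**What to change.** In 13.7, state that the final DLT rate at the MTD will be reported for all DLT-evaluable patients treated at that dose, from dose finding and expansion together, with an exact 95% interval, beside the model estimate and its interval.

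In 5.3 and 13.3, use one definition: a patient with a cycle-1 DLT is DLT-evaluable regardless of doses received; a patient without a DLT needs at least 2 of 3 selinexor and 19 of 21 ibrutinib doses.

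This takes a few sentences, with no extra patients or visits. The price is the chance worked out above that an acceptable dose shows a pooled rate of 30% or more: about 7-8% at a true 0.20 and 15-17% at 0.25. Such a result would be reported with its interval and would not by itself stop accrual or reverse the dose. Showing the pooled rate to the DSMC before Cohort 3 opens would be sensible but is optional.
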